## 12. Care for the safety of the participants

#### 12.1 Definition of safety-related terms

The safety-related terms of this clinical trial are defined in accordance with the Good Clinical Practice Act (Rules on the Safety of Drugs).

#### 1) Definition of Adverse Event (AE)

Undesirable and unintended signs (e.g., abnormal laboratory test results), symptoms, or diseases that occur during the administration or use of a drug, etc. and are not necessarily causally related to the investigational drug.

## 2) Definition of Adverse Drug Reaction (ADR)

An ADR refers to a harmful and unintentional reaction caused by normal administration and use of a drug, and its causal relationship with the drug cannot be excluded. If the causal relationship with the drug is not known among the voluntarily reported adverse events, it is considered an adverse drug reaction. However, if both the reporter and the manufacturer/client determine that it is not related to the drug, it shall be excluded as an adverse drug reaction.

#### 3) Serious AE/ADR (Serious AE/ADR)

Serious AE/ADR refers to an adverse event or adverse drug reaction that falls under any of the following categories:

- 1 A case that results in death or is life-threatening
- 2 A case that requires hospitalization or an extension of the hospitalization period
- 3 Cases that result in persistent or severe disability or diminished function
- (4) Cases resulting in congenital deformities or abnormalities
- (5) In addition to cases ①~④, other medically significant circumstances, such as the development of drug dependence, abuse, or blood disorders, that occur and require treatment.

The following events are not considered serious adverse reactions:

- ① Routine treatment or monitoring of the investigational indications that are not associated with worsening of the condition
- ② Procedures for protocol/disease-related investigations (however, hospitalization or prolongation of hospitalization due to complications of such procedures shall be considered an SAE)
- 3 Hospitalization or prolongation of hospitalization for technical, practical, or social reasons in the absence of an adverse event
- 4 Voluntary treatment of a pre-existing condition unrelated to the indication for which the study is being conducted
- (5) Emergency treatment or observation as an outpatient that did not result in hospitalization
- (6) Hospitalization or prolongation of hospitalization due to a plan (i.e., scheduled prior to the start of the study)
- (7) Hospitalization not for the purpose of improving or treating poor health conditions (e.g., nursing care and administrative reasons).

However, the occurrence of major ischemic and hemorrhagic events, or any hospitalization or procedure resulting from them, will not be considered a serious adverse event, given the underlying condition of the patient in this study:

- Death
- MI
- Repeat revascularization
- Stent thrombosis
- CVA/Stroke
- Bleeding (BARC 2-5)

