# 5. Study population

Patients with varicose veins of lower extremities will be enrolled.

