#### 7.3. Visit 3 (Midterm Assessment Visit, 6 weeks from randomization visit)

- 1) Lower extremity venous Doppler ultrasound (required)
- 2) Assessment of symptoms: Venous Clinical Severity Score (VCSS), CIVIQ-14
- 3) Performance of blood tests, urinalysis (optional)
- 4) Concomitant medications check (antiplatelet, antithrombotic, antihyperlipidemic).
- 5) Review of lifestyle therapy frequency of stocking wear, pharmacotherapy medication adherence checks
- 6) Monitoring of adverse events

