#### 8.2. Medical History and Prior/Concomitant Medications

Medical history is defined as any medical condition that has been ongoing for less than 1 year as of Visit 1 (screening start date), including past medical history (hypertension, diabetes, hyperlipidemia, previous PCI, previous myocardial infarction, peripheral vascular disease, heart failure, CVA, dialysis, CABG) and clinically significant diagnostic findings from blood chemistry, urinalysis, physical examination, endoscopy, etc. performed up to Visit 2. In addition, the history of medications within 4 weeks (28 days) of Visit 1 (screening start date) and up to Visit 2 will be investigated and collected as prior medications, and the history of medications at Visit 2 will be collected as concomitant medications.

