#### 12.3.8 Reporting of Serious Adverse Events

If a Serious Adverse Event occurs, the Principal Investigator must notify the IRB within 72 h in accordance with the institution's SOPs.

For all serious and unexpected adverse events, the Principal Investigator must report to the IRB and the Commissioner of Food and Drug Safety in accordance with the Rules for the Safety of Drugs and Other Medicinal Products and Good Clinical Practice for Pharmaceuticals, Item 8.

Provide as complete information as possible, but at a minimum include the following information:

- 1) The patient to whom the SAE occurred (identification number)
- 2) The suspect drug
- 3) The source of the information (investigator)

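### Section 12.1 classes fatal, life-threatening and hospitalized cases as serious, then removes death, MI, stroke and BARC 2-5 bleeding from that class, and so from expedited reporting

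*Combined protocol and SAP*

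**What the plan says.** Section 12.1, item 3, gives five criteria for a serious adverse event or reaction. The first is "A case that results in death or is life-threatening"; the second covers hospitalization or its prolongation. After a list of routine exceptions, the item adds another: "the occurrence of major ischemic and hemorrhagic events, or any hospitalization or procedure resulting from them, will not be considered a serious adverse event", with the reason "given the underlying condition of the patient in this study". Six items follow: death, MI, repeat revascularization, stent thrombosis, CVA/stroke and bleeding of BARC grade 2-5.

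Section 12.3.8 sets two reporting routes. The first reads "If a Serious Adverse Event occurs, the Principal Investigator must notify the IRB within 72 h". The second reads "For all serious and unexpected adverse events, the Principal Investigator must report to the IRB and the Commissioner of Food and Drug Safety".

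Section 5 describes the population: "Patients with varicose veins of lower extremities will be enrolled".

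There is also a difference over when adverse event collection starts. Section 12.3.7 starts it once study medication has begun. Note c to the schedule in section 14 starts it at signature of consent, and the schedule marks adverse event investigation at Visits 1 to 4. The adverse event definition in section 12.1, item 1, refers to events during use of a drug.

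**The concern.** Death is both the first criterion for seriousness and the first item on the list of events that are not serious. Site staff facing a fatal stroke would find one sentence making it an SAE and another saying it is not.

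Such an exception can be defended when the excepted events are endpoints collected and reviewed by another route. That is not so here. The primary endpoint is venous reflux time, and the secondary endpoints in section 3.4 are ultrasound measures, extracellular water ratio, VCSS and CIVIQ-14. The appeal to the underlying condition does not fit varicose veins: stent thrombosis and repeat revascularization correspond to no eligibility criterion or endpoint in this protocol.

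If the exception is followed, the most important safety events of the trial go to the CRF without prompt outside review. The documents describe no data monitoring committee that would see them early.

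**Working it through.** The plan states no figure to reproduce. The check sets the rules side by side and follows each event through to reporting.

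**Step 1: the definition against the exception.**

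| Event | Under the SAE criteria | Under the exception |
|---|---|---|
| Death | Serious (criterion 1) | Not serious |
| MI, stroke, stent thrombosis, BARC 2-5 bleeding | Serious if fatal, life-threatening or hospitalized, or if another criterion is met | Not serious |
| Repeat revascularization | Serious if it requires or prolongs hospitalization, or if another criterion is met | Not serious |
| Hospitalization resulting from any of these | Serious (criterion 2) | Not serious |

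For death the conflict is direct. For the other events it arises whenever a criterion is met, because the exception also removes the hospitalization that would have met it.

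**Step 2: from definition to reporting.** The 72-hour IRB notice requires an SAE. The regulator report requires an event that is both serious and unexpected. An excepted event is not serious, so on the literal text it enters neither route. The IRB notice is lost for every excepted event that meets a seriousness criterion. The regulator report is lost only for those that are also unexpected. CRF recording (sections 12.2 and 12.3.7) and follow-up (section 12.3.5) remain. No section gives these events another expedited route.

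**Step 3: can the events occur in this trial?** Section 8.2 collects "previous PCI, previous myocardial infarction, peripheral vascular disease, heart failure, CVA, dialysis, CABG" as medical history. Section 6.1.2 excludes heart failure and lower-limb arterial occlusive disease, but not prior PCI, MI, CVA or CABG. Section 7.3 includes a "Concomitant medications check (antiplatelet, antithrombotic, antihyperlipidemic)", and section 7.4 repeats it. Patients may be enrolled up to, but not including, age 80. The exception can therefore apply to enrolled patients.

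**Step 4: how many reports are at stake?** The documents give no event rate, so 1, 2 and 5 excepted events per 100 patient-years are assumed.

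- Follow-up from randomization: 200 × 12 / 52.18 = 46 patient-years.
- Expected events = 46 × rate / 100 = 0.46, 0.92 and 2.3.
- Chance of at least one (Poisson) = 1 − exp(−expected) = 37%, 60% and 90%.

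Counting from consent adds the 2 to 4 weeks of screening, for a nominal window of 14 to 16 weeks:

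- 200 × 14 / 52.18 = 53.7 and 200 × 16 / 52.18 = 61.3 patient-years.
- At 1 per 100: 0.54 to 0.61 events. At 5 per 100: 2.7 to 3.1 events.

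These figures ignore dropout, which the plan sets at 20%, and so are slightly high.

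**Step 5: the start of adverse event collection.** Section 12.3.7 gives about 12 weeks in the 100 test patients and no defined start in the 100 control patients, who take no study medication. Note c gives 14 to 16 weeks in both arms. Visit 4 may move by 14 days either way.

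**The case against.** The strongest objection is that reporting does not rest on this text alone. Section 12.1 says its terms follow the national Good Clinical Practice rules, and section 12.3.8 refers to those rules and to the institution's procedures. They may require a report whatever the exception says. This is possible, but the rules are not in the documents and cannot be checked. If they do require a report, the protocol tells staff the opposite, which is itself a reason to correct it.

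Second, the exception is introduced as covering ischemic and hemorrhagic events, so death may mean only death from those causes. The list item carries no such limit, and even the narrow reading takes fatal events out of criterion 1.

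Third, the practical reach may be small. Stent thrombosis and repeat revascularization presuppose an earlier procedure, not every BARC 2-5 bleed would have been serious, and the exclusions lower the risk. This stands as a limit on numbers. The assumed rates are illustrative, and the contradiction does not depend on them.

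Fourth, deletion is not the only remedy: the exception could be kept with its own expedited route. That is true, but nothing in the documents gives a reason to keep it.

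Finally, the start-date conflict is a separate and milder matter. Note c does give a start for all patients, and Visits 3 and 4 include adverse event monitoring without distinction by arm. This stands: the missing start for controls is a defect of section 12.3.7, not of the whole plan.

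**Conclusion.** The concern holds and must be fixed. Section 12.1, item 3, contradicts itself. On the protocol's own wording, six event categories are taken out of SAE status for all 200 planned patients. For deaths, this covers at least those from ischemic or hemorrhagic causes and, read literally, any death. The loss is the 72-hour IRB notice and, for unexpected events, the regulator report. The CRF record is kept, and the primary analysis is unaffected.

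The contradiction rests only on the text. The likely number of affected events, about 0.5 to 3, rests on assumed rates. Whether outside rules would still compel reporting is unknown. The conflict over the start of adverse event collection is real but secondary; in an open-label comparison with a no-drug arm it risks uneven ascertainment.

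**What to change.** Delete the exception for major ischemic and hemorrhagic events in section 12.1, item 3, together with its six-item list. The general SAE definition and section 12.3.8 then apply to every event.

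In the same amendment, reconcile section 12.1 (item 1), section 12.3.7 and note c in section 14 to one start point for both arms; note c already names consent. Reword the adverse event definition so that it also covers patients who take no study drug.

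The cost is one amendment that removes one paragraph and its list and aligns two sentences. No visits, tests or staff are added, and the sample size and analysis do not change. The added workload is the few SAE reports estimated above.

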#### 12.2 Recording of Adverse Events

Symptoms and signs of adverse events, related actions, date of onset, severity or criticality of the adverse event, severity (maximum intensity), course, causality to the investigational product, and outcomes should be recorded in the CRF, including details of dose changes and

treatment, if necessary. Adverse events identified at previous visits should be followed up at subsequent visits, and follow-up of adverse events should be documented in the CRF.

#### 12.3 Evaluation of Adverse Events

#### 12.3.1 Assessing the severity of an AE

The severity of an AE is categorized according to the following criteria based on maximal intensity:

1=Mild: An AE that is barely noticeable by the patient, does not interfere with normal daily activities (functioning), and most often does not require treatment.

2=Moderate: Patients may feel discomfort and interference with normal daily activities (functioning); patients may be able to continue the study but may require treatment.

3=Severe: Extremely uncomfortable and interferes with normal daily activities (functioning), may prevent the patient from continuing to participate in the study and may require treatment or hospitalization.

#### 12.3.2 Assessing the Causal Relationship of Adverse Events to the Investigational Product

The causal relationship to the study medicinal product will be categorized into six levels as follows and the opinion of the principal investigator or study staff will be recorded, if necessary. All but "unlikely" of the causal relationships will be evaluated as adverse drug reactions in which a causal relationship with the study drug cannot be excluded.

#### 1) Certain

The relationship between the administration and use of the drug product is plausible and not explained by other drugs, chemicals, or concomitant conditions; the response is clinically plausible upon discontinuation of the drug product and pharmacologically or phenomenologically conclusive upon reintroduction of the drug product, as needed.

#### 2) Fairly certain (Probable/Likely)

The temporal relationship between the administration and use of medicinal products is reasonable and does not appear to be due to other medicinal products, chemicals, or concomitant conditions. There is a clinically reasonable response to the discontinuation of the medicinal product (no re-dosing information).

#### 3) Possible

The temporal relationship between the administration and use of the medicinal product is reasonable, but can also be explained by other medicines, chemicals, or concomitant conditions, and information on the discontinuation of the medicinal product is lacking or unclear.

#### 4) Unlikely

A temporary case is unlikely to be causally related to the administration or use of the drug and can be reasonably explained by other drugs, chemicals, or potential diseases.

#### 5) Evaluation difficulties (Conditional/Unclassified)

More information is needed for a proper evaluation or additional information is being reviewed.

#### 6) Unassessable/Unclassifiable

Insufficient or conflicting information is available to make a judgment and cannot be supplemented or confirmed.

The relationship between an adverse event and the investigational drug (or other causes, progression of the underlying disease, concomitant treatment, etc.) will be determined based on how well the adverse event can be explained based on the clinical judgment of the principal investigator and staff, in terms of the following:

- 1) The known pharmacologic actions of the investigational drug
- 2) Similar actions previously observed with the investigational drug or drugs in the same class of drugs
- 3) Reactions that have been frequently reported to be associated with similar drugs (e.g., blood disorders)
- 4) Reactions that appear to be time-related (disappear when the drug is discontinued and reappear when the drug is restarted).

#### 12.3.3 Actions Taken Regarding Adverse Events

Actions taken in response to adverse events can be categorized into those related to the investigational medicinal product and those unrelated to the investigational medicinal product as follows:

#### 1) Investigational drug measures

- ① Discontinuation: Discontinuation of an investigational drug due to a specific adverse reaction
- ② Dose maintenance: Continued administration of an investigational drug because of an adverse event that does not require discontinuation.
- 3 The reason for discontinuing an investigational drug owing to an adverse event is unknown (e.g., loss of contact with the patient).
- 4 Not applicable: Discontinued the investigational drug for reasons other than the specific adverse event (e.g., study termination or discontinuation of the investigational drug before the adverse event occurred).

#### 2) Other actions

- 1 No action taken (no action taken)
- 2 Concomitant medication taken (concomitant medication taken)
- 3 Non-drug therapy given (non-drug therapy given)
- 4 Etc (comments)

#### 12.3.4 Outcome of the adverse event

- 1) Recovered/Resolved (Recovered/Resolved)
- 2) Recovering/Resolving(Recovering/Resolving)
- 3) Not recovered/Not resolved (Not recovered/Not resolved)
- 4) Recovered with sequelae/Resolved but with sequelae (Recovered with sequelae)
- 5) Fatal damage (Fatal)
- 6) Death may be related to AE (Death unrelated to AE)
- 7) Death unrelated to AE (Death unrelated to AE)
- 8) Unknown (Unknown)

#### 12.3.5 Follow-up of Adverse Events

The Principal Investigator or study staff should follow patients with adverse events until the symptoms subside, abnormal clinical laboratory values return to baseline, or there is a satisfactory explanation for the observed changes. The progression of the AE should be documented in the supporting documentation and CRF.

## 12.3.6 Progression of Adverse Events

- 1) Continuous: All events except one and intermittent.
- 2) Intermittent: Adverse events that occur occasionally or events that occur repeatedly over a continuous period of time.
- 3) Single-episode: an adverse event occurred only once.

#### 12.3.7 Reporting of Adverse Events

All AEs that occur during the study, even if unrelated to the investigational product, will be recorded in detail in the CRF, including symptoms and signs, onset/end date, severity, treatment and course, relationship with the investigational product, and significance. The collection of AEs begins after the initiation of the study medication and continues until the patient's last visit (or last contact) or early termination visit.

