## 4. Research protocol and trial design

This study is designed as an investigator-initiated, single-center, open-label, pragmatic, randomized controlled trial. Patients with symptoms of lower extremity discomfort and leg edema and demonstrable venous reflux on lower extremity venous Doppler ultrasound ( $\geq 0.5$  seconds in superficial veins or  $\geq 1$  s in deep veins) will be screened for inclusion in the study. All patients who meet the inclusion criteria will be considered for inclusion.

[figure not shown]
Patients who are eligible for randomization will be randomized 1:1 to the therapeutic lifestyle change (TLC) only arm (control arm) or the medication (Entelon®) plus TLC arm (test arm). The patients will be treated for 12 weeks according to their assigned treatment arms. Patients will be evaluated for improvement in venous reflux in the target vessels and symptomatic improvement using lower-extremity venous Doppler ultrasonography at 6 and 12 weeks post-treatment.

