#### 4.4. Medication + TLC group

Patients selected for the combined approach of pharmacotherapy and lifestyle modifications will receive Entelon® 150 mg twice daily for a duration of 12 weeks. This pharmacological intervention should be complemented by the adoption of improved lifestyle habits, including wearing compression stockings.

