# 14. Study schedule

	Baseline	Period			
Study Visit	V1	V2	V3	V4	
Period	Run-in/ Screening	Baseline	Interim Assessment	Closing	
Week/Day	-4~-2W	Day 0	6W(±14D)	12W(±14D)	
Written Informed Consenta	•				
Grant Screening No.	•				
Check inclusion/exclusion criteria	•	•			
Demographic Survey	•				
Drug administration history survey b	•	•			
Randomization (assignment of registration number)		•			
Lower extremity venous Doppler ultrasound examination	•		•	•	
Blood test and urinalysis	•		•	•	
Symptoms: VCSS, CIVIQ-14	•		•	•	
Medication history survey	•	•	•	•	
Adverse event investigations	•	•	•	•	

- a. No procedures in this study may be initiated prior to obtaining informed consent.
- b. Previous medications will be investigated and recorded only for medications used within 1 month prior to obtaining informed consent.
- c. Adverse events will be investigated after the first study-related procedure (i.e., date of signature of informed consent) until the last assessment date.

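### Section 12.3.7 starts adverse-event collection at a first dose that the TLC-only arm never takes, and conflicts with the consent-based start in the study schedule

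*Combined protocol and SAP*

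**What the plan says.** Two places in the current text set the start of AE collection.

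- Section 12.3.7 (Reporting of Adverse Events): "The collection of AEs begins after the initiation of the study medication and continues until the patient's last visit". The rest of the sentence adds last contact or an early termination visit as alternative end points.
- Section 14 (Study schedule), footnote c: "Adverse events will be investigated after the first study-related procedure (i.e., date of signature of informed consent) until the last assessment date".

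The arms differ in whether they ever receive the drug. Under section 4, patients are "randomized 1:1 to the therapeutic lifestyle change (TLC) only arm (control arm) or the medication (Entelon®) plus TLC arm (test arm". Under section 4.4, the medication group "will receive Entelon® 150 mg twice daily for a duration of 12 weeks". Section 4.3 gives the TLC group lifestyle measures and no study drug.

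Three further passages bear on scope.

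- The sentence that opens 12.3.7: "All AEs that occur during the study, even if unrelated to the investigational product, will be recorded in detail in the CRF".
- The AE definition in section 12.1, which covers events "that occur during the administration or use of a drug, etc. and are not necessarily causally related to the investigational drug".
- The visit procedures. Sections 7.3 and 7.4 list AE monitoring at Visits 3 and 4 with no restriction by arm, and the schedule table marks AE investigations at all four visits.

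**The concern.** AE frequencies in two arms can be set against each other only if events were sought over the same period and in the same way in both. A start rule that hangs on the first dose cannot do that here, because the event that opens the window never happens in the control arm. Site staff who follow 12.3.7 have no date from which to collect in those patients. Staff who follow footnote c start at consent. The trial is open-label (section 4.2), so those recording events know who is untreated and could apply a drug-based rule differently by arm without noticing.

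Control-arm events are the only concurrent background against which drug-arm events can be read. If they are under-recorded, the gap cannot be repaired after the trial ends. The run-in adds a second problem. Inclusion criterion 3 requires at least 4 weeks off analgesics, steroids, anti-inflammatory and venoactive drugs by Visit 2, and events in the part of that period after consent are inside one window and outside the other.

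**Working it through.** The plan gives no figure to reproduce. The check sets the passages side by side and then sizes the conflict from the plan's own numbers.

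**Inputs**
- Planned size: 100 per arm, 200 in total (section 11.1).
- Screening to randomisation: 2 to 4 weeks (section 7.1 and schedule).
- Randomisation to end visit: 12 weeks (section 7.4).
- Study drug: medication plus TLC arm only (sections 4 and 4.4).

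**Step 1. When does the window open?**

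| Source | Drug arm | TLC-only arm |
|---|---|---|
| 12.3.7, start sentence | First dose | No start point |
| Schedule, footnote c | Consent | Consent |

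Both are current text, and a site cannot follow both.

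**Step 2. Does other wording settle it?** Only in part.
- The opening sentence of 12.3.7 covers the whole study and removes any causality filter, but gives no start date.
- The AE definition refers to use of a drug. Read strictly, an event in an untreated patient might not qualify. The definition says a drug and then etc., not the study drug, so it leaves room.
- Visits 3 and 4 list AE monitoring for everyone. The lists for Visits 1 and 2 (sections 7.1 and 7.2) contain none, whereas the schedule marks AE investigations at both. For the period before treatment, sections 7.1, 7.2 and 12.3.7 therefore point one way and the schedule the other.

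**Step 3. Size.** Assume full recruitment, no dropout, first dose on the day of Visit 2, and nominal visit dates (the ±14-day windows are ignored).
- Patients with no defined start under 12.3.7 read alone: 100/200 = 50%.
- Window under 12.3.7: drug arm 100 × 12 = 1,200 patient-weeks; control arm undefined.
- Window under footnote c: 100 × (12 + 2) = 1,400 to 100 × (12 + 4) = 1,600 patient-weeks in each arm.
- Time counted under footnote c but not under 12.3.7 in the drug arm: 100 × 2 = 200 to 100 × 4 = 400 patient-weeks, which is 2/12 = 17% to 4/12 = 33% on top of the treatment period.
- From randomisation onward in both arms: 100 × 12 = 1,200 patient-weeks each. This is the period in which the arms differ in treatment and can be observed equally.

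**The case against.** A reader might infer from 12.3.7 that the control arm will have no safety data. The documents do not support that. It follows only if one sentence is read in isolation. The sentence before it, the Visit 3 and 4 procedures and the schedule all require AE recording without regard to arm, and section 8.3 plans vital signs and physical examinations at each visit for everyone.

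Three other strong readings also fail.

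- **A planned comparison is biased.** Section 11.2 specifies no between-arm AE analysis, and no AE endpoint is listed. What is at risk is whatever safety summary is reported.
- **Serious events in control patients escape IRB reporting.** Section 12.3.8 has its own trigger, the occurrence of a serious event, with a 72-hour deadline. It does not refer to the 12.3.7 window.
- **The extra 17% to 33% of observation time distorts the comparison.** Under footnote c that time comes before randomisation and is the same in both arms, so it produces no difference between them by itself.

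It is also fair to say that the AE definition sets no clock, and that section 12.1 ties the safety terms to the governing GCP rules, so the definition cannot simply be rewritten at will.

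These points limit the consequence. They do not remove the conflict: two start rules stand in the current text, and the one in the section that governs AE reporting has no application to half the patients.

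**Conclusion.** The inconsistency is certain on the text. Section 12.3.7 gives no AE start for 100 of 200 planned patients and contradicts footnote c. The consequence is a risk, not a certainty: control-arm AEs may be missed, or ascertained differently from drug-arm AEs, in a trial where staff know the allocation. How large the effect would be depends on which rule the site follows, and the documents do not say. If footnote c were applied to everyone, both arms would have the same window.

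Events in the 2 to 4 weeks between consent and randomisation are counted or not according to the rule chosen. That affects the AE totals in both arms rather than the contrast between them.

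This should be fixed. It touches no efficacy endpoint and no planned test, but it bears on the safety data, and the remedy is already half-written in the schedule.

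**What to change.** 1. In section 12.3.7, replace the start sentence with one rule for both arms that agrees with footnote c: AEs are collected from signature of informed consent to the last visit or last contact, identically in each arm.
2. Add AE monitoring to the Visit 1 and Visit 2 lists in sections 7.1 and 7.2, so that they match the schedule.
3. State in section 11.2 that any between-arm AE summary counts events from randomisation (Visit 2) onward, with earlier events listed separately.
4. In section 12.1, add a line that the AE definition applies to every enrolled patient whatever the arm, worded consistently with the governing rules cited there.

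The cost is a few sentences of protocol wording and a few more AE entries in the CRF. No visit or test is added, since the schedule already marks AE investigations at all four visits.
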